8.3.1.1 Molecular response

Molecular response (MR) will be assessed in all patients.

Levels of BCR-ABL1 transcripts will be determined by real-time quantitative PCR (RQ-PCR) testing of peripheral blood and analyzed centrally. Log reduction in BCR- ABL1 transcripts levels from the standardized baseline value, or the percent ratio of BCR-ABL1 transcripts versus control gene (ABL1) transcripts converted to a reference standard, international scale (IS) ([Hughes and Branford 2006](#)), will be calculated for each sample.

Major molecular response and related variables are defined as the following:

- Rate of MMR where MMR is defined as a ≥ 3.0 log reduction in BCR-ABL1 transcripts compared to the standardized baseline equivalent to ≤ 0.1 % BCR-ABL1/ABL1 % by IS as measured by RQ-PCR, confirmed by duplicate analysis of the same sample,
- Time to MMR defined as the time from the date of enrollment to the date of the first documented MMR,
- Duration of MMR defined as the time from the date of first documented MMR to the earliest date of loss of MMR, progression to AP or BC, or CML-related death.
- Rate of Deep Molecular Responses MR4 and MR4.5 are defined as a ≥ 4 log or ≥ 4.5 log reduction in BCR-ABL1 transcripts compared to the standard baseline equivalent to 0.01 % or 0.0032% BCR-ABL1/ABL by IS as measured by RQ-PCR, confirmed by duplicate analysis of the same sample with at least 10,000 or 32,000 ABL1 transcripts, respectively.

Loss of MMR is defined as increase of BCR-ABL1/ABL to $> 0.1\%$ by international scale (IS) in association with a ≥ 5 -fold rise in BCR-ABL1 from the lowest value achieved on study

treatment and replicated by a second analysis of the same sample. Loss of MMR confirmed by subsequent sample analysis within 4 to 6 weeks showing loss of MMR associated with a ≥ 5 -fold rise in BCR-ABL1 from the lowest value achieved on study treatment, unless it is associated with confirmed loss of CHR or loss of CCyR or progression to AP/BC or CML-related death. The blood samples will be taken as described in [Table 8-1](#) and [Table 8-2](#).

If at one visit the sample is missing during transit to the central PCR laboratory, or the PCR result is difficult to interpret or sample not analyzable, or if the PCR sample was not collected, a subsequent unscheduled visit sample must be collected within 4 weeks either at the next scheduled visit (week 4 or week 8) or as an unscheduled visit.

Table 8-2 Blood samples (efficacy primary endpoint)

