2.1 Data analysis general information

The planned analyses will be performed by Novartis. SAS version 9.4 or later will be used to perform all data analyses and to generate tables, figures and listings.

No formal interim analysis is planned for this trial. The following analyses are planned as detailed below.

- 48-week primary analysis: Formal testing of the primary endpoint will be performed. Analyses of other efficacy endpoints at and by week 48 and safety analyses will also be performed.
- 96-week analysis: Analyses of efficacy endpoints at and by week 96 and safety analyses will be performed.
- End of study treatment analysis is similar to the 96-week analysis without formal statistical testing. All efficacy and safety analyses will be included.

Except where categorically stated, all analyses, including the primary analysis will be conducted on **all** participant data (excluding the additional subjects who were intolerant to the last TKI and were in MMR at baseline). The purpose of having two randomized groups is not for comparison, but to provide data on different dosing regimens. Randomization is only used to have a balance in the allocation of treatment into either asciminib 40 mg b.i.d. or 80 mg q.d.

Data included in the analyses

The analysis data cut-off dates for the planned analyses are:

- 48-week Primary analysis: After all randomized subjects have been on study treatment for 48 weeks or discontinued earlier, i.e., LPFT + 48 weeks.

- 96-week analysis: After all randomized subjects have been on study treatment for 96 weeks or discontinued earlier, i.e., LPFT + 96 weeks.
- End of study treatment analysis: 30 days after the EOsT. (Note: After the study treatment period, every effort will be made to continue provision of the study treatment to subjects who in the opinion of the investigators are still deriving clinical benefit through alternative options if asciminib is not commercially available).

All statistical analyses will be performed using all data collected in the database up to the respective data cut-off date. All data with an assessment date or event start date (e.g. vital sign assessment date or start date of an adverse event) prior to or on the cut-off date will be included in the analysis. Any data collected beyond the cut-off date will not be included in the analysis and will not be used for any derivations.

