The reference start date for safety assessments (e.g. adverse event onset, laboratory abnormality occurrence, vital sign measurement, dose interruption, etc.) is the start of study treatment.

The reference start date for all other, non-safety assessments (e.g. molecular response, disease progression, ECOG performance status, patient reported outcomes (PRO), etc.) is the date of randomization.

The reference start date for dose escalation (200 mg q.d.) is the date when a subject starts first escalated dose.

The study day will be displayed in the data listings. If an event starts before the reference start date, the study day displayed on the listing will be negative.

Time unit

A year length is defined as 365.25 days. A month length is 30.4375 (=365.25/12) days. If duration is reported in months, duration in days will be divided by 30.4375. If duration is reported in years, duration in days will be divided by 365.25.

A week length is defined as 7 days. If duration is reported in weeks, duration in days will be divided by 7.

Baseline for the treatment period

For efficacy evaluations, the last non-missing assessment, including unscheduled assessments on or before the date of randomization is taken as “baseline” value or “baseline” assessment. In the context of baseline definition, the efficacy evaluations also include PRO and performance status.

For safety evaluations, the last available assessment, including unscheduled assessments before the date of start of study treatment is taken as “baseline” assessment.

For pre-dose electrocardiogram (ECG), the last available assessment before the treatment start date is used for baseline.

For ECGs requiring triplicate measures per time point, the average of these measurements will be reported by sites in eCRF baseline.

For mutations, the screening/baseline assessment is taken as “baseline” assessment.

In rare cases where multiple laboratory measurements meet the baseline definition, with no further flag or label that can identify the chronological order, then the following rule should be applied: If values are from central and local laboratories, the value from central assessment should be considered as baseline.

If subjects have no value as defined above, the baseline result will be missing.

On-treatment assessment/event and observation periods

For adverse event reporting the overall observation period will be divided into three mutually exclusive segments:

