1. ***pre-treatment period:*** from day of subject’s informed consent to the day before first administration of study treatment
2. ***on-treatment period:*** from date of first administration of study treatment to 30 days after date of last administration of study treatment (including start and stop date).
3. ***post-treatment period:*** starting at day 31 after last administration of study treatment.

If dates are incomplete in a way that clear assignment to pre-, on-, post-treatment period cannot be made, then the respective data will be assigned to the on-treatment period.

Safety summaries (tables, figures) on the corresponding Safety set include only data from the on-treatment period with the exception of baseline data which will also be summarized where appropriate (e.g. change from baseline summaries). In particular, summary tables for adverse events (AEs) will summarize only on-treatment events, with a start date during the on-treatment period. In addition, a separate summary for death will be provided.

However, all safety data (including those from the pre-treatment and post-treatment) will be listed and flagged as appropriate.

Efficacy summaries on the FAS and FAS 2 (apart from OS and PFS) include data from baseline up to either the last assessment on or before the End of Treatment (EoT) visit or before or on treatment failure, whichever is the earliest.

The efficacy assessments collected post-treatment failure or post-EoT visit are not included in any efficacy analyses (except for OS and PFS analyses). However, they will be listed and flagged as appropriate.

Windows for multiple assessments

Data such as molecular response, cytogenetic response collected over time (including unscheduled visits) will be summarized by scheduled time point. As subjects do not always adhere to the visit schedule, visits will be remapped according to visit windows defined in Tables 2-1 to Table 2-3 of this document to enable by-visit analysis. Only those protocol-defined visits will have the visit window defined. Each assessment (including the end of treatment assessment), either scheduled or unscheduled, will have a mapped visit assigned, as long as study day is available, according to the defined visit window up to the date with data included.

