If more than one assessment is assigned to the same time window, the assessment performed closest to the target date will be used for by-visit statistical analyses. If 2 assessments within a visit window are equidistant from the target date, then the average of the 2 assessments will be used. If multiple assessments are on the same date, then the the average will be used. Data from all assessments (scheduled and unscheduled), including multiple assessments, will be listed.

Table 2-1 Time windows for molecular response

Assessment	Target day of assessment	Time Interval
Baseline	≤ 1	\leq Day 1 [#]
Week 12	85	Day 2 to day 127
Week 24	169	Day 128 to day 211
Week 36	253	Day 212 to day 295
Week 48	337	Day 296 to day 379
Week k (k=60, 72, ...)	$K \times 7 + 1$	Day $k \times 7 - 40$ – $k \times 7 + 43$

Day 1 = Date of randomization
EOT assessments are mapped to the time points as needed.

Table 2-2 Time windows for cytogenetic response

Assessment	Target day of assessment	Time Interval
Baseline	1	≤ Day 1 [#]
Week 48	337	Day 253 to day 420
EOT [*]	EOT	EOT

[#] Day 1 = Date of randomization. Should bone marrow assessments have been performed before the main informed consent is signed but within 56 days of Week 1 Day 1, no further bone marrow sampling will be required at screening and local assessment data will be collected.

^{*} Only required for Early Discontinuation due to lack of response / loss of response

For PRO data time windows will be defined for descriptive summary by visit. If more than one assessment is available in the same time window, the assessment closest to the planned date will be considered. If two assessments are obtained with the same time difference compared to the scheduled visit day, the assessment obtained prior to visit will be considered.

Table 2-3 Time windows for PRO: MDASI-CML

Assessment	Target day of assessment	Time Interval
Baseline	1	≤ Day 1 [#]
Week 4	29	Day 2 to day 57
Week 12	85	Day 58 to day 127
Week 24	169	Day 128 to day 253
Week 48	337	Day 254 to day 421
Week 72	505	Day 422 to day 589
Week 96	673	Day 590 to day 757
Week 120	841	Day 758 to day 925
EOT (Week 144)	1009	Day 926 to day 1009

[#] Day 1 = Date of randomization

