2.5 Analysis supporting primary objective(s)

In this section, the targeted treatment effect corresponding to the primary objective as well as the primary objective is clarified using the estimand language.

The primary clinical question of interest is: What is the effect of asciminib in CML subjects in chronic phase who were resistant or intolerant to 2 or more prior TKIs, with regards to achieving MMR at 48 weeks while on study treatment regardless of dose modification, dose interruption, or any intake of concomitant medications and without intake of prohibited medications.

The primary estimand is described by the following attributes:

1. The target population comprises CML Subjects with resistance or intolerance to 2 or more prior TKI per the 2020 ELN recommendations.
2. Endpoint: Major Molecular Response (MMR) achieved at week 48 while on study treatment without meeting any treatment failure criteria prior to week 48. A subject will be counted as having achieved MMR at week 48 if he/she meets the MMR criterion ($BCR::ABL1 \leq 0.1\% IS$) at week 48 while on study treatment unless the subject met any treatment failure criteria prior to week 48.

3. Treatment of interest: the investigational treatment asciminib received for at least 48 weeks, with or without dose modification, dose interruption or any intake of concomitant medications, or intake of prohibited medications.
4. The intercurrent events are the events occurring after first dose of study drug that may impact the treatment effect. The intercurrent events of interest are:
 - a) Treatment discontinuation (i.e. having performed an EOT visit) prior to week 48 due to any reason
 - b) Dose modification or dose interruption, or any intake of concomitant medications
 - c) Intake of prohibited medications
5. The summary measure is the MMR rate and its 95% confidence interval at week 48.

The primary analysis will be conducted after all randomized subjects have been on study treatment for 48 weeks or discontinued earlier, i.e., LPFT + 48 weeks.

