2.5.4 Handling of missing values not related to intercurrent event

Subjects with missing PCR evaluations at 48 weeks will be considered as non-responders. However, if the 48-week PCR evaluation is missing, but both a PCR evaluation at 36 weeks and a PCR evaluation at 60 weeks indicate MMR, the 48-week assessment is imputed as a 'Response', assuming that MMR is maintained between 36 and 60 weeks.

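### The primary cut-off of LPFT + 48 weeks falls on the last starter's Week-48 target day, so a compliant late or replacement PCR can be shut out of the primary endpoint

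*SAP*

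**What the plan says.** - **Cut-off.** SAP 2.1 places the 48-week primary analysis "After all randomized subjects have been on study treatment for 48 weeks or discontinued earlier, i.e., LPFT + 48 weeks". SAP 2.5 repeats the condition: "The primary analysis will be conducted after all randomized subjects have been on study treatment for 48 weeks or discontinued earlier". LPFT is not in the SAP's list of abbreviations.
- **Data after the cut-off.** Data dated on or before the cut-off count. For the rest, SAP 2.1 says: "Any data collected beyond the cut-off date will not be included in the analysis and will not be used for any derivations". PCR results are not exempted anywhere.
- **Visit window.** Protocol Section 8 and Table 8-1 put the Week-48 visit at Day 337, plus or minus 7 days.
- **Replacement PCR.** If a sample is missing, not analysable, hard to interpret or not collected, Protocol 8.3.1.1 says "a subsequent unscheduled visit sample must be collected within 4 weeks either at the next scheduled visit" or at an unscheduled visit.
- **Analysis window.** SAP 2.1.1 states: "As subjects do not always adhere to the visit schedule, visits will be remapped according to visit windows". The Week-48 molecular window in SAP Table 2-1 is "Day 296 to day 379", counted from randomization. If several results fall in a window, the one closest to the target day is used.
- **Missing data.** SAP 2.5.4: "Subjects with missing PCR evaluations at 48 weeks will be considered as non-responders". The one exception needs MMR at both Week 36 and Week 60.

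**The concern.** The cut-off has no allowance after the target day, although the protocol gives the visit 7 further days and a failed sample 4 further weeks. For the last subjects to start, whether a compliant sample counts can depend on which side of the target day it fell. These subjects may still be on treatment with no intercurrent event, so a non-response score would come from the calendar and not from the estimand. The analysis concerned is the only one with a formal test. By contrast, the end-of-study-treatment cut-off in the same section has a 30-day allowance.

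**Working it through.** **1. The plan's own figure.** Inputs from SAP Section 3: n = 156, null rate 0.23, alternative 0.33, one-sided alpha 0.025, exact test. P(X ≥ 47 | 156, 0.23) = 0.0241 and P(X ≥ 46) = 0.0363, so rejection needs 47/156 (30.1%). The Clopper-Pearson lower bound is 23.05% at 47/156 and 22.47% at 46/156, so both rejection rules agree. Power = P(X ≥ 47 | 156, 0.33) = 0.801, which reproduces the stated 80%.

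**2. Day arithmetic.** The Week-48 target is 48 × 7 + 1 = Day 337, and LPFT + 336 days is Day 337 of the last starter. A subject first dosed s days before LPFT is at Day 337 + s at the cut-off, so a sample on Day D is excluded if s < D − 337. Week 1 Day 1 is taken as the first-dose day.

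| Sample | Latest day D | Can be lost if s is below |
|---|---|---|
| Week-48 visit at the end of its window | 344 | 7 |
| Replacement after a target-day visit | 337 + 28 = 365 | 28 |
| Replacement after a Day-344 visit | 344 + 28 = 372 | 35 |
| End of SAP Week-48 window | 379 | 42 − L |
| First day of SAP Week-60 window (60 × 7 − 40) | 380 | 43 − L |

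L is the lag in days from randomization to first dose. It enters only the last two rows, because SAP windows run from randomization. The last row shows why the Week-36/60 rule cannot help these subjects. The fourth row concerns remapped samples, not a visit that the protocol permits.

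**3. What happens to the score.**
- *No other PCR from Day 296 to the cut-off:* the subject is a non-responder even if the excluded sample shows MMR. Protocol Table 8-2 schedules no PCR between Week 36 and Week 48, so this is the usual case.
- *An earlier unscheduled PCR in that span:* it becomes the Week-48 value. Suppose Day 300 is in MMR and Day 340 is not. With all data, Day 340 is closer to target (3 days against 37) and the subject is a non-responder. With the cut-off at Day 337, only Day 300 remains and the subject is a responder. Conversely, 0.15% on Day 300 and 0.08% on Day 340 turns a responder into a non-responder.

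**4. Cost per subject.** With k subjects forced to non-response, power = P(X ≥ 47 | 156 − k, 0.33). The same formula at 0.23 gives the actual alpha.

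| k | Power | Actual alpha |
|---|---|---|
| 0 | 80.1% | 0.0241 |
| 1 | 78.5% | 0.0216 |
| 2 | 76.9% | 0.0192 |

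Each lost responder lowers the observed rate by 1/156 = 0.64 points.

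**5. How many subjects.** The documents give no accrual, lateness or sample-loss rates. Assumptions: even accrual over 9 to 24 months; 25% to 50% of visits 1 to 7 days late, evenly spread; 2% to 5% of samples replaced, all 28 days after target (pessimistic); no earlier PCR in the window.
- FAS starts per day: 156/(9 × 30.44) = 0.569 down to 156/(24 × 30.44) = 0.214. This gives 4.0 to 1.5 starts in the last 7 days.
- Late visits lost: rate × late share × Σ(7 − s)/7 for s = 0 to 6, and the sum is 4. Low 0.214 × 0.25 × 4 = 0.21; high 0.569 × 0.50 × 4 = 1.14.
- Replacements lost: rate × 28 × share. Low 0.214 × 28 × 0.02 = 0.12; high 0.569 × 28 × 0.05 = 0.80.
- Total: 0.33 to 1.94 results. At a 33% response rate, 0.11 to 0.64 responders.

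A second set of assumptions for the visit window alone: 1 to 3 starters in the last week, the last-treated patient in the FAS, and visits even over Days 330 to 344. It gives 7/15 = 0.47 to 7/15 + 2 × 4/15 = 1.0 results, 0.15 to 0.33 responders, and power of 79.4% to 78.5%.

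**The case against.** **The wording can be read as a minimum.** Both SAP 2.1 and SAP 2.5 say the analysis comes after everyone has had 48 weeks, which would permit a later date. But SAP 2.1 then equates this with LPFT + 48 weeks. If a later date was intended, the SAP does not give it.

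**There may be some slack.** Day-337 samples count, Days 330 to 337 are compliant, and sites are asked to keep visits close to the designated day. The cut-off is tied to all randomized subjects, so if the last starter is in the MMR-at-baseline cohort, the primary population gains some days. A lag from randomization to dosing relaxes the SAP-window limits, but not the 7-day and 28-to-35-day limits if Week 1 Day 1 is the first dose. This reduces the number affected but does not remove the gap.

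**The data are reported elsewhere.** SAP 5.5.1 shows ongoing subjects without a Week-48 result separately, and later samples enter the 96-week data. That helps transparency, but the formal test is unchanged. Neither sensitivity analysis in SAP 2.5.5 restores the samples: one removes the Week-36/60 imputation, the other drops only COVID-19 missingness.

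**The size rests on assumptions.** This stands in full. A reader might infer that several late responders will be lost; every scenario above expects fewer than one.

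**Conclusion.** The gap is real and follows from the text, given the reading of LPFT as last patient first treatment. Its main effect is conservative and small: about 0 to 2 results and fewer than one expected responder, under assumed rates. It would alter the conclusion only at the boundary between 46 and 47 responders, although planned power of 80.1% leaves almost no margin above the 80% target.

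A reader might also infer that the rule can only lower the MMR rate and so carries no false-positive risk. The documents do not support that. Under the closest-to-target rule, an early unscheduled PCR can replace an excluded later one in either direction. This should be rare, and the power and alpha figures above, which model forced non-response only, do not include it. The point is a cheap improvement, not a threat to the validity of the trial.

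**What to change.** In SAP 2.1, before the first database lock, define LPFT and set one fixed primary cut-off for all data, including PCR, treatment status and treatment failure:

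- **At least LPFT + 49 weeks** (49 × 7 + 1 = Day 344): covers every compliant Week-48 visit, but not replacement samples.
- **Preferably LPFT + 53 weeks** (Day 372): also covers replacement PCRs.
- **Or LPFT + 54 weeks** (Day 379): covers the whole SAP Week-48 window.

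Keeping the present cut-off and admitting only later PCR samples would not work. The endpoint requires response on study treatment and without prior treatment failure, and neither could be established at a sample dated after the cut-off for those data.

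The cost is one or two sentences in the SAP and a read-out delayed by 1, 5 or 6 weeks respectively. Even at LPFT + 54 weeks the Week-36/60 rule stays out of reach for the last starter, because its Week-60 window opens on Day 380. By then, however, the Week-48 window has been observed in full.

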2.1.1 General definitions

Investigational drug and study treatment

Investigational drug, will refer to asciminib. No additional treatment beyond investigational drug is included in this trial.

Treatment groups

- Asciminib 40 mg b.i.d. (Subjects randomized to asciminib 40 mg b.i.d. at the beginning of the study)
- Asciminib 80 mg q.d. (Subjects randomized to asciminib 80 mg q.d. at the beginning of the study)

The standard dose for all subjects in this study is asciminib 40 mg b.i.d. or 80 mg q.d. For subjects not achieving MMR at 48 weeks or losing the response after the week 48 assessment up to week 108, a dose escalation to 200 mg q.d. may be considered per investigator decision.

Date of end of study treatment (EOsT)

The EOsT date is the date that the study treatment is ended for the entire study. On this date, subjects are treated for at maximum 144 weeks, unless subjects have discontinued study treatment earlier.

Date of first administration of study treatment

The date of first administration of study treatment is derived as the first date when a non-zero dose of study treatment was administered as per the Study Treatment electronic case report form (eCRF). The date of first administration of study treatment will also be referred as start of study treatment.

The date of first administration of study treatment is the same as the date of first administration of investigational drug.

Start Date of dose escalation

The start date of dose escalation is derived as the first date when a subject had dose escalated to 200 mg q.d. of study treatment as per the Subject Status Dose Escalation case report form (eCRF).

Date of last administration of study treatment

The date of last administration of study treatment is defined as the last date when a non-zero dose of study treatment was administered as per Study Treatment eCRF.

The date of last administration of study treatment is the same as the date of last administration of investigational drug.

Study day

The study day, describes the day of the event or assessment date, relative to the reference start date.

The study day is defined as:

- The date of the event (visit date, onset date of an event, assessment date, etc.) – reference start date + 1 if event is on or after the reference start date;
- The date of the event (visit date, onset date of an event, assessment date, etc.) – reference start date if event precedes the reference start date.

The reference start date for safety assessments (e.g. adverse event onset, laboratory abnormality occurrence, vital sign measurement, dose interruption, etc.) is the start of study treatment.

The reference start date for all other, non-safety assessments (e.g. molecular response, disease progression, ECOG performance status, patient reported outcomes (PRO), etc.) is the date of randomization.

The reference start date for dose escalation (200 mg q.d.) is the date when a subject starts first escalated dose.

The study day will be displayed in the data listings. If an event starts before the reference start date, the study day displayed on the listing will be negative.

Time unit

A year length is defined as 365.25 days. A month length is 30.4375 (=365.25/12) days. If duration is reported in months, duration in days will be divided by 30.4375. If duration is reported in years, duration in days will be divided by 365.25.

A week length is defined as 7 days. If duration is reported in weeks, duration in days will be divided by 7.

Baseline for the treatment period

For efficacy evaluations, the last non-missing assessment, including unscheduled assessments on or before the date of randomization is taken as “baseline” value or “baseline” assessment. In the context of baseline definition, the efficacy evaluations also include PRO and performance status.

For safety evaluations, the last available assessment, including unscheduled assessments before the date of start of study treatment is taken as “baseline” assessment.

For pre-dose electrocardiogram (ECG), the last available assessment before the treatment start date is used for baseline.

For ECGs requiring triplicate measures per time point, the average of these measurements will be reported by sites in eCRF baseline.

For mutations, the screening/baseline assessment is taken as “baseline” assessment.

In rare cases where multiple laboratory measurements meet the baseline definition, with no further flag or label that can identify the chronological order, then the following rule should be applied: If values are from central and local laboratories, the value from central assessment should be considered as baseline.

If subjects have no value as defined above, the baseline result will be missing.

On-treatment assessment/event and observation periods

For adverse event reporting the overall observation period will be divided into three mutually exclusive segments:

1. ***pre-treatment period:*** from day of subject’s informed consent to the day before first administration of study treatment
2. ***on-treatment period:*** from date of first administration of study treatment to 30 days after date of last administration of study treatment (including start and stop date).
3. ***post-treatment period:*** starting at day 31 after last administration of study treatment.

If dates are incomplete in a way that clear assignment to pre-, on-, post-treatment period cannot be made, then the respective data will be assigned to the on-treatment period.

Safety summaries (tables, figures) on the corresponding Safety set include only data from the on-treatment period with the exception of baseline data which will also be summarized where appropriate (e.g. change from baseline summaries). In particular, summary tables for adverse events (AEs) will summarize only on-treatment events, with a start date during the on-treatment period. In addition, a separate summary for death will be provided.

However, all safety data (including those from the pre-treatment and post-treatment) will be listed and flagged as appropriate.

Efficacy summaries on the FAS and FAS 2 (apart from OS and PFS) include data from baseline up to either the last assessment on or before the End of Treatment (EoT) visit or before or on treatment failure, whichever is the earliest.

The efficacy assessments collected post-treatment failure or post-EoT visit are not included in any efficacy analyses (except for OS and PFS analyses). However, they will be listed and flagged as appropriate.

Windows for multiple assessments

Data such as molecular response, cytogenetic response collected over time (including unscheduled visits) will be summarized by scheduled time point. As subjects do not always adhere to the visit schedule, visits will be remapped according to visit windows defined in Tables 2-1 to Table 2-3 of this document to enable by-visit analysis. Only those protocol-defined visits will have the visit window defined. Each assessment (including the end of treatment assessment), either scheduled or unscheduled, will have a mapped visit assigned, as long as study day is available, according to the defined visit window up to the date with data included.

If more than one assessment is assigned to the same time window, the assessment performed closest to the target date will be used for by-visit statistical analyses. If 2 assessments within a visit window are equidistant from the target date, then the average of the 2 assessments will be used. If multiple assessments are on the same date, then the the average will be used. Data from all assessments (scheduled and unscheduled), including multiple assessments, will be listed.

Table 2-1 Time windows for molecular response

Assessment	Target day of assessment	Time Interval
Baseline	≤ 1	\leq Day 1 [#]
Week 12	85	Day 2 to day 127
Week 24	169	Day 128 to day 211
Week 36	253	Day 212 to day 295
Week 48	337	Day 296 to day 379
Week k (k=60, 72, ...)	$K \times 7 + 1$	Day $k \times 7 - 40$ – $k \times 7 + 43$

Day 1 = Date of randomization
EOT assessments are mapped to the time points as needed.

Table 2-2 Time windows for cytogenetic response

Assessment	Target day of assessment	Time Interval
Baseline	1	≤ Day 1 [#]
Week 48	337	Day 253 to day 420
EOT [*]	EOT	EOT

[#] Day 1 = Date of randomization. Should bone marrow assessments have been performed before the main informed consent is signed but within 56 days of Week 1 Day 1, no further bone marrow sampling will be required at screening and local assessment data will be collected.

^{*} Only required for Early Discontinuation due to lack of response / loss of response

For PRO data time windows will be defined for descriptive summary by visit. If more than one assessment is available in the same time window, the assessment closest to the planned date will be considered. If two assessments are obtained with the same time difference compared to the scheduled visit day, the assessment obtained prior to visit will be considered.

Table 2-3 Time windows for PRO: MDASI-CML

Assessment	Target day of assessment	Time Interval
Baseline	1	≤ Day 1 [#]
Week 4	29	Day 2 to day 57
Week 12	85	Day 58 to day 127
Week 24	169	Day 128 to day 253
Week 48	337	Day 254 to day 421
Week 72	505	Day 422 to day 589
Week 96	673	Day 590 to day 757
Week 120	841	Day 758 to day 925
EOT (Week 144)	1009	Day 926 to day 1009

[#] Day 1 = Date of randomization

The general rule for the target day of assessment and time interval is: For Week k visit, target day of assessment is defined as $k*7+1$. For the time interval, “Lower limit” = “upper limit of prior applicable visit” +1. “Upper limit” = “target day of current visit” + integer part of (“target day of next applicable visit” – “target day of current visit”)/2.

Last contact date

The last contact date will be derived for subjects not known to have died at the respective analysis data cut-off date using the last complete date among the following:

Table 2-4 Last contact date data sources

Source data	Conditions
Date of randomization	No condition
Start/End dates from further antineoplastic therapy	Non-missing medication/procedure term
Start/End dates from drug administration record	Non-missing dose. Doses of 0 are allowed
Study disposition date	The date of the subject's last protocol assessment performed in the study phase
Any specific efficacy (molecular or cytogenetic) assessment date if available	Evaluation is marked as 'done'
Laboratory/PK collection dates	Sample collection marked as 'done'
Vital signs date	At least one non-missing parameter value
Performance status date	Non-missing performance status
Start/End dates of AE	Non-missing verbatim term

The last contact date is defined as the latest complete date from the above list on or before the respective data cut-off date. The cut-off date will not be used for last contact date, unless the subject was seen or contacted on that date. No date post the cut-off date will be used. Completely imputed dates (e.g. the analysis data cut-off date programmatically imputed to replace the missing end date of a dose administration record) will not be used to derive the last contact date.

The last contact date will be used for censoring of subjects in the analysis of overall survival.

